7.4 Subject Population(s) for Analysis

All participants will be used in analysis. Intention to treat analysis will be used to avoid the effects of crossover and dropout providing unbiased comparisons among the treatment groups.

8 Safety and Adverse Events

Any complications will be treated in the usual way irrespective of study arm included in.

The Chief Investigator will be continuously monitoring the data and if sequentially the first 4 (15%) patients in the non-fasting group show signs of an event rate in excess of that shown in the fasting group, as demonstrated by non-overlapping confidence intervals then stopping rules will be applied.

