2.2 Study Objectives

- To show that allowing patients to eat freely up to the point of elective coronary angiography/angioplasty is not associated with any increased risk of nausea, vomiting, abdominal pain, emergency intubation or aspiration pneumonia compared to patients kept nil by mouth.
- To show improved patient satisfaction when allowed to eat up to the point of elective coronary angiography/angioplasty compared to patients kept nil by mouth.

We aim to provide evidence from a prospective study to help the development of guidelines that can be implemented nationally and internationally regarding pre procedural care of cardiac patients.

3 Study Design

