3.2 Study procedure

All patients to be admitted electively for coronary angiography or angioplasty will be given the opportunity to participate. An invitation letter together with patient information leaflet outlining the study will be sent along with the pre-procedure appointment letter to give the patient time to read and think about the study. Once at pre-procedure assessment clinic, the study will be explained further including potential risks and intended outcome and patients concerns will be addressed. Patient will be given the opportunity either to take part in the study or abstain and follow the standard procedure. If the patient agrees then they will sign the consent form and then be randomised in a 1:1 ratio to either the fasting or non-fasting group and be allocated a patient identification number. This will be done at the pre-procedure assessment clinic.

1- Fasting group (current practice): Clear fluids up to the time of the procedure and no food for at least 2 hours before the procedure.

2-Non Fasting Group: Clear fluids and food up to the time of the procedure.

The pre procedure preparation will then be documented in the notes. Intention to treat analysis will be used to avoid the effects of crossover and dropout providing unbiased comparisons among the treatment groups.

The case report form (CRF) will be appended inside the front cover of the notes to be completed on the day of procedure by the operating physician and the remainder completed by the research team. Finally once the patient is ready for discharge they will be asked to complete an anonymous questionnaire relating to their experience and satisfaction.

A database will be composed on an encrypted flash drive and backed up on the catheter lab computer. Only the patient identification number will be included in this but will still be password protected.

All patients will be contacted by phone on day 30 or the nearest working day thereafter to ensure no chest infections.

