4.1 Subject Selection and Withdrawal

Once enrolled in the study all patients will be identified by their study number alone and the arm of the study they are involved in. If the patient decides to withdraw from the study at any point after randomization, they will revert to the standard hospital procedure policy of fasting. However, they will still be included in the final analysis as intention to treat and any drop out or cross over will be documented.

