4.5 Withdrawal of Subjects

If any patient chooses to withdraw from the study, they will revert to the standard hospital procedure. However, they will still be included in the final analysis as intention to treat and any drop out or cross over will be documented.

5 Prior and Concomitant Therapy

All previous medication and treatments should continue.

6 Clinical Procedure

As standard practice, operators will be allowed to use any techniques they commonly use throughout their practice (choice of access, balloon and stent type).

7 Statistical Plan

Given that the occurrence of pulmonary aspiration was so low in similar studies performed for cerebral angiography, we decided against using this as a single primary endpoint as thousands of patients would be required. We opted for a composite primary end point of nausea, vomiting, abdominal pain, emergency intubation and aspiration. These will be recorded both immediately intra/post procedure by the operation physician and again by the patient within 8 hours after the procedure. We will compare the two groups using 95% confidence intervals to ascertain the extent to which they overlap. Secondary end points will be overall patient satisfaction, the incidence of hypoglycaemia and hypotension, and 30 day chest infection rate which will be compared between the two groups.

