7.1 Sample Size Determination

With 200 participants in each group, if none of the participants has an event then the upper limit of the 95% confidence interval for event rate would be 1.5%. Hence if both groups, fasting and non-fasting, have no events recorded then it is highly unlikely that the event rate in the two groups would differ by more than 1.5%. Provided that a difference of 1.5% in event rate is deemed not clinically meaningfully different; then 200 participants in each group would demonstrate that not fasting has a similar event rate to fasting.

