9.3 Records Retention

All records will be archived for 5 years in line with the Trust R&D Policy.

10 Study Monitoring, Auditing, and Inspecting

The investigator will permit study-related monitoring, audits and inspections by the Ethics Committee, the Sponsor and the Research Governance Manager.

Participation as an investigator in this study implies adherence to the principles and responsibilities of the Research Governance Framework, ICH/GCP and Directive 2000/20/EC

11 Ethical Considerations

The patient will receive a detailed description of the study in the patient information sheet send together with pre-procedure assessment letter by mail (around 1 week before the pre-procedure assessment clinic date) to give him/her time to think about the study. Then, at the pre-procedure assessment clinic, they will have the opportunity to ask questions with one of the research team and to answer any queries. Any patient will have the right to abstain from taking part into the study or to withdraw after taking part without affecting the standard of care they are receiving.

The Chief Investigator will ensure that the risk of the study does not outweigh the benefit at any point during the study time, and if so, the study will be prematurely terminated.

The benefit /risk of taking part into the study will be adequately explained to the patients. There will be no direct benefit to the patient from taking part in this study. However, the information gained from the study will help improve the quality of service offered to the patients, increase their satisfaction, may aid in changing the current practice and avoiding unnecessary delay to the patients. The potential risk will be made clear which is the occurrence of nausea and vomiting at an expected rate of 1-2% and no expected emergency endotracheal intubation or aspiration pneumonia cases.

Once patient is enrolled in the study, all his personal information will be anonymized with the only identifier the study number. All patient data will be password protected on the computer in the cath lab. All health professionals involved in the study and patient care will have access to this

information if required. Only the CI will have access to identify the patient personal data for the purpose of safety.

To ensure un-biased result, an adequate randomization process with intention to treat analysis will be undertaken. Analysis will be done by the Sub-Investigator who is blinded to group allocation.

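### ITT compares the assigned policies without bias but does not avoid crossover, as sections 3.2 and 7.4 say it does; no analysis of actual food intake is specified

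*Combined protocol and SAP*

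**What the plan says.** Section 3.2 states that "Intention to treat analysis will be used to avoid the effects of crossover and dropout", and section 7.4 repeats the sentence in full: "Intention to treat analysis will be used to avoid the effects of crossover and dropout providing unbiased comparisons among the treatment groups". Section 7.4 has one analysis population, containing every participant.

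The objective in section 2.2 is to show that "allowing patients to eat freely up to the point of elective coronary angiography/angioplasty is not associated with any increased risk". Section 7.1 sets the scale of the claim: "Provided that a difference of 1.5% in event rate is deemed not clinically meaningfully different".

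Four features of the plan bear on what patients will actually have eaten:

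- In section 3.2 the fasting arm has "no food for at least 2 hours before the procedure". The non-fasting arm is permitted food but not required to take it.
- Under section 4.1, when patients withdraw after randomisation, "they will revert to the standard hospital procedure policy of fasting". They remain in their assigned arm for analysis.
- Section 4.5 adds that "any drop out or cross over will be documented", and section 3.2 has the preparation written in the notes.
- The background (section 2.1) reports that patients commonly fast for longer than they were told to, and gives loss of appetite before a procedure as one reason.

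The opening of section 7 and sections 7.2 and 7.4 do not say how recorded preparation or crossover will enter the analysis or the report.

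**The concern.** ITT prevents the selection bias that comes from excluding or reclassifying patients after randomisation. It does not take crossover out of the comparison. A patient assigned to food who then fasted is still counted as non-fasting, so the contrast in eating between the arms is smaller than the contrast in assignment.

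Two routes lead there. The plan creates one itself, because withdrawals from the non-fasting arm return to fasting. The other is simple non-eating. Such patients are following the policy, but they say nothing about the risk of a procedure soon after food.

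In a trial aiming to show a difference, this shrinkage works against the sponsor. Here the aim is to show no increased risk, so it works in favour of the hoped-for conclusion. If no excess is seen and uptake is not reported, the result supports a policy of allowing food at an unknown uptake. It can then easily be over-read as showing that eating up to the procedure carries no excess risk.

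**Working it through.** **Inputs from the documents.** 200 patients per arm; an upper limit of 1.5% with no events; 1.5 points as the difference conditionally treated as unimportant (all section 7.1); a 2-hour food limit in the fasting arm (section 3.2).

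**Input not in the documents.** The share c of the non-fasting arm that does not eat. No withdrawal, crossover or non-eating rate is given, so c = 5 to 30% is an assumption.

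**The plan's own figure.** The rule of three gives 3/200 = 1.50%. The exact one-sided 95% limit is 1 - 0.05^(1/200) = 1.49%. The stated 1.5% reproduces, with no allowance for crossover.

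**Dilution.** Suppose assignment affects outcome only through eating and nobody in the fasting arm eats within the limit. Then

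ITT difference = (1 - c) × true excess among those who ate,

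so the true excess that shows as 1.5 points is 1.5/(1 - c). The last column below assumes event rates of 1.5% when eating and 0% when fasting; the chance of no events in the non-fasting arm is then (1 - 0.015(1 - c))^200.

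| c (assumed) | Ate, of 200 | ITT value of a true 1.5-point excess | True excess showing as 1.5 points | Chance of 0/200 |
|---|---|---|---|---|
| 0% | 200 | 1.50 | 1.50 | 4.9% |
| 5% | 190 | 1.43 | 1.58 | 5.7% |
| 10% | 180 | 1.35 | 1.67 | 6.6% |
| 20% | 160 | 1.20 | 1.88 | 8.9% |
| 30% | 140 | 1.05 | 2.14 | 12.1% |

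Applying the rule of three to those who ate (3/190, 3/180, 3/160, 3/140) gives 1.58, 1.67, 1.88 and 2.14%. This is the same arithmetic as 1.5/(1 - c), not separate evidence.

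If 5% of the fasting arm also ate within the limit (a further assumption), the figure at c = 20% becomes 1.5/(1 - 0.20 - 0.05) = 2.00 points.

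**Why eaters should not simply be compared with fasted patients.** Assume 20% do not eat, the overall fasted risk is 1%, and eaters have a 3-point excess. Let the fasted risk of the non-eaters be 1, 2, 3 or 4%. The ITT difference is 0.8 × 3 = 2.4 points each time, and 2.4/0.8 recovers 3.00. Eaters against the whole fasting arm give 3.00, 2.75, 2.50 and 2.25, because the eaters are a selected group.

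**Limit of the scaled estimate.** Dividing the ITT difference by the between-arm difference in food within 2 hours treats 2 hours as the only boundary that matters. Assume instead that any food within 6 hours adds 2 points. In the non-fasting arm 40% eat within 2 hours and 40% at 2 to 6 hours; in the fasting arm 30% eat at 2 to 6 hours and none later. The ITT difference is 2 × (0.80 - 0.30) = 1.0, and 1.0/0.40 = 2.5, not 2. If nobody in the fasting arm ate within 6 hours, it is 2 × 0.80/0.40 = 4.0. The estimate therefore needs a second assumption about earlier food.

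**The case against.** The strongest reply is that the sentence is only loosely worded. Read with its second half, it may mean no more than that ITT avoids the bias of dropping or moving crossovers, which is true. The objective concerns allowing food, so a patient who is allowed to eat and does not is complying, and ITT answers that question directly. Both points stand, and they are why ITT should remain primary. They do not make it true that crossover effects are avoided, and they do not tell a reader how much eating took place.

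The size of the problem is also open to challenge. It rests wholly on an assumed c, and at 5-10% the shift is only 0.08 to 0.17 points. With 0/200 against 0/200 events and no crossover at all, the two-sided 95% Newcombe interval for the difference is already ±1.88 points, beyond 1.5. Precision is the larger limit at low c. This stands too.

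A reader might infer that intake will go unrecorded. The documents do not support that: preparation, drop-out and crossover are to be documented, and the case report form is not among the documents, so time of last food may already be captured. What can be said is that no analysis of intake is specified.

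A reader might also infer that ITT should give way to a per-protocol or as-treated analysis, or that a no-increased-risk claim should need both to agree. The policy objective does not require this, and eaters against fasted patients is a comparison selected on behaviour after randomisation.

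**Conclusion.** The point holds as a correction of a stated property and a gap in reporting. It is not a fault in the choice of primary analysis. ITT is unbiased for the assigned policies but keeps crossover, and the plan's own withdrawal rule produces crossover in the direction that favours the hoped-for result.

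The size cannot be fixed from the documents. Under assumed non-eating of 5, 10, 20 or 30%, a true excess of 1.58, 1.67, 1.88 or 2.14 points would show as 1.5. That is minor at the low end and worth knowing at the high end. Dilution toward no difference assumes that permission without eating has no effect on outcome.

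It would go too far to infer that a finding of no excess would be invalid, or that harm is being hidden. The finding would be valid for allowing food at whatever uptake occurred, and the documents give no reason to assume that uptake will be low enough to matter greatly. The change is one to consider: it is cheap, and it settles what the trial can conclude.

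**What to change.** 1. Keep ITT as the primary analysis. In sections 3.2 and 7.4 replace the sentence with: *Patients will be analysed by assigned group (ITT). This gives an unbiased estimate of the policy of allowing food; crossover and non-eating dilute any effect of eating itself toward no difference.*
2. Make sure time of last food is recorded in both arms, in the part of the case report form that the research team completes, so that the operator does not see it.
3. Report by arm the distribution of time since last food, the share with food within 2 hours of the procedure (the plan's own limit for the fasting arm), withdrawals and crossovers, and the number with time missing.
4. Word the conclusion as the effect of allowing food at the observed uptake.
5. Optional: a supportive estimate, the ITT risk difference divided by the between-arm difference in uptake. If used, state how missing times are handled and state both assumptions: permission without eating has no effect, and food taken before the chosen cut-off has no effect or is equally common in both arms. It is not a condition of the claim.

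Section 11 says "Analysis will be done by the Sub-Investigator who is blinded to group allocation". Intake data would reveal the arms, so produce items 3 and 5 after the ITT result is fixed.

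The cost is at most one form field, one table and two sentence edits. The optional estimate has an interval wider than the ITT one by 1/(1 - c), that is 1.05, 1.11, 1.25 or 1.43 times at c = 5, 10, 20 or 30%. With no events in either arm, ±1.88 points becomes ±1.98, 2.09, 2.36 or 2.69.

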8.1 Recording of Adverse Events

All adverse events occurring during the study period will be recorded. The clinical course of each event will be followed until resolution, stabilisation, or until it has been determined that the study treatment or participation is not the cause. Serious adverse events that are still ongoing at the end of the study period will be followed up to determine the final outcome. The cardiac anaesthetic team has been made aware of the study in case a non-fasting patient need to be taken for emergency surgery.

8.2 Expected non-serious Adverse Events

The following are expected non-serious events and will be recorded on the Case Report Form and reported to the CI as necessary. They do not need to be reported to the sponsor.

These include:

- Nausea and vomiting.
- Abdominal pain
- Procedure-related transient bradycardia (HR<60 bpm).
- Procedure-related transient hypotension (SBP<90 mmHg).
- Puncture site related hematoma/ecchymosis.

8.3 Serious Adverse Events (SAEs)

All SAEs will be recorded on the Case Report Form and reported to the CI within 7 days. The CI will be responsible for the prompt notification of findings that could adversely affect the health of patients or impact on the conduct of the trial. Only unexpected SAEs or fatal events will be

reported to the Sponsor immediately (maximum within 15 days). The sponsor will report events to the REC as necessary (usually only events that are both related to the intervention and unexpected).

The following information will be collected for each serious adverse event:

- Whether the event is considered expected or unexpected
- Full details in medical terms and case description
- Event duration (start and end dates, if applicable)
- Action taken
- Outcome
- Causality in the opinion of the investigator

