8.5 Unexpected and fatal Serious Adverse Events

- Emergency endotracheal intubation.
- Pulmonary aspiration.
- All other serious adverse events that are not listed under " expected SAEs".
- Events that results into death.

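### Section 8.3 allows 7 days to tell the Chief Investigator of an aspiration or emergency intubation, although the Chief Investigator is the trial's only safety monitor; a 24-hour limit would cost almost nothing

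*Combined protocol and SAP*

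**What the plan says.** Section 8.3 sets one limit for telling the CI, whatever the event: "All SAEs will be recorded on the Case Report Form and reported to the CI within 7 days". Section 8.5 lists "Emergency endotracheal intubation" and "Pulmonary aspiration" among the unexpected SAEs, so the limit covers both, in either arm.

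Other provisions bear on the same events:

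- Section 8.3 has unexpected or fatal SAEs "reported to the Sponsor immediately (maximum within 15 days").
- Section 8.3 also says: "The CI will be responsible for the prompt notification of findings that could adversely affect the health of patients".
- The opening of section 8 says: "The Chief Investigator will be continuously monitoring the data". It ties this to a stopping rule on the first 4 non-fasting patients. Section 7.3 has a similar rule on the first 10, also monitored by the CI. Both act when confidence intervals do not overlap.
- Section 11 says: "The Chief Investigator will ensure that the risk of the study does not outweigh the benefit at any point during the study time", and that the study ends early if it does.
- Section 3.2 has the operating physician complete the case report form on the day. The form is kept in the patient's notes.
- Section 8.1 says that the cardiac anaesthetic team knows of the study.

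Under section 11, patients are told that there are "no expected emergency endotracheal intubation or aspiration pneumonia cases".

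**The concern.** Aspiration and emergency intubation are the serious components of the primary endpoint and the harms that fasting is meant to prevent. The person who must judge whether the study should go on is the CI; no monitoring committee is described. Yet the only stated time for these events to reach the CI is the one that applies to every other SAE.

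The CI's duties to notify promptly and to end the study can begin only once the CI knows of the case, and neither has a time limit or a single-event trigger. In the worst case that the text permits, patients would go on eating up to their procedures for a week after an event that participants were told was not expected. Only patient safety is at stake, and only if such an event happens.

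**Working it through.** The plan gives no figure for exposure during a reporting delay, so there is none to reproduce.

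**1. Which limits apply to whom**

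| Provision | Recipient or actor | Time stated | Study decision attached |
|---|---|---|---|
| 8.3, all SAEs | CI | 7 days | none |
| 8.3, unexpected or fatal SAEs | Sponsor | immediately, at most 15 days | none |
| 8.3, harmful findings | by the CI | prompt, no number | none |
| 8 and 7.3, stopping rules | by the CI | none | stop if intervals separate |
| 11, risk against benefit | by the CI | at any point | stop, no named trigger |

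The 7 days is the only stated limit for informing the CI.

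**2. Non-fasting patients treated during the delay**

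Inputs: 400 patients, 1:1 allocation, so 200 non-fasting; duration 12 months (section 1). Even accrual is an assumption, because no weekly rate is given. Formula: 200 × days of delay / days of recruitment.

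- 12 months: 200 × 7 / 365.25 = 3.8; in 1 day, 0.55; in 2 days (one more day for a decision), 1.1.
- If the 12 months includes the last patient's 30-day follow-up: 200 × 7 / 335.25 = 4.2.
- If the two-month window in section 4.1.1 is the recruitment period (61 days): 200 × 7 / 61 = 23; in 1 day, 3.3.

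These are averages, not upper limits.

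**3. Expected harm**

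Section 2.1 cites a registry of 1916 non-fasted PCI patients with no immediate intubation and no aspiration pneumonia. The upper 95% limit is 3/1916 = 0.157% (rule of three) or 1 − 0.025^(1/1916) = 0.192% (exact, two-sided).

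- Chance of at least one case in 200: 1 − (1 − 0.00157)^200 = 27%, or 32% at 0.192%.
- Expected further cases in 3.83 patients: 0.0060 to 0.0074. Multiplied by the chance of a first case: 0.0016 to 0.0024 over the trial.
- With 23 patients: 0.036 to 0.044, and 0.010 to 0.014 over the trial.

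These rates are upper limits, not estimates. Section 2.1 also puts aspiration after emergency bypass surgery or DC conversion in unfasted patients in the order of 0.001%. At that rate the chance of any aspiration in 200 patients is 1 − (1 − 0.00001)^200 = 0.2%.

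**4. Can the stopping rules respond to one case?**

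The interval method is not named, so three are tried, with no fasting events and equal arms.

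| Arms | Method | Upper limit, 0 events | Lower limit, 1 event | Events needed to separate |
|---|---|---|---|---|
| 4 v 4 | Exact | 60.2% | 0.6% | none suffices |
| 4 v 4 | Wilson | 49.0% | 4.6% | 4 |
| 4 v 4 | Wald | 0% | below 0 | 2 |
| 10 v 10 | Exact | 30.8% | 0.3% | 7 |
| 10 v 10 | Wilson | 27.8% | 1.8% | 6 |
| 10 v 10 | Wald | 0% | below 0 | 3 |

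Wald, 2 of 4: 0.50 − 1.96 × 0.25 = 0.01, just above 0. Wald, 1 of 4: 0.25 − 1.96 × 0.217 = −0.17. Wald, 1 of 10: 0.10 − 1.96 × 0.095 = −0.09. One case on its own triggers neither rule under any of the three methods.

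**The case against.** The best counter-argument is that a faster route already exists. Aspiration and intubation are named as unexpected, unexpected SAEs go to the sponsor immediately, and the sponsor is the Trust that runs this single-centre study. The operator fills in the form the same day, and the CI monitors continuously. In practice the CI may well hear within hours. The gain is also slight: section 3.2 asks for only 2 hours without food, so a pause would restore a modest protection, and only if the CI chose one.

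Much of this stands, and it makes the point minor. It does not remove it: the sponsor route carries no duty to tell the CI, and its only number is 15 days.

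A reader might infer more than the documents support:

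- **That nothing allows the study to be stopped.** Section 11 gives the CI that duty, and section 3.5 foresees early termination for safety. What is missing is a short deadline for telling the CI and a review after a single case.
- **That the CI will not know for a week.** Seven days is the permitted maximum, not the expected delay.
- **That the stopping rules cannot respond to two cases.** Under the first-4 rule with Wald intervals, 2 of 4 against 0 of 4 does separate.
- **That only non-fasting cases need the faster limit.** A one-arm trigger would require the reporter to know the allocation, despite the investigator blinding in section 1, and would scrutinise primary-endpoint components unequally between arms.

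**Conclusion.** The point holds as a minor patient-safety improvement. The 7-day limit is out of step with the protocol's own treatment of these events as unexpected and immediately reportable to the sponsor, and it applies to the one person who monitors safety.

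Compared with 24-hour notice, it leaves on average about 3 more non-fasting patients treated before the CI must be told (3.8 − 0.5), or about 20 on the two-month reading (23 − 3.3). Both figures assume even accrual. Even at the registry's upper limits, the further cases expected over the whole trial are about 0.002 on 12-month accrual and at most about 0.014 on the two-month reading. Not all of these would be averted, since that also needs a decision to pause. The trial's conclusions are unaffected.

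**What to change.** Amend section 8.3 to read:

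> Any pulmonary aspiration, emergency endotracheal intubation or other unexpected or fatal SAE, in either arm, is reported to the CI within 24 hours of the study team becoming aware of it; all other SAEs within 7 days. For an aspiration or emergency intubation the CI promptly reviews allocation and causality and records whether the study continues, pauses or stops.

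Starting the clock at awareness covers a case that first comes to light at the day-30 call. Reporting comes before the causality judgement, so a doubtful case does not fall back to 7 days. No pause is automatic. Anyone moved to standard fasting during a pause is analysed as randomised, as sections 4.1, 4.5 and 7.4 already provide.

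The cost is two sentences and slightly more reporting work. The CI sees the allocation for that one case; section 11 assigns the analysis to a blinded Sub-Investigator, which limits the effect on blinding. A pause would affect about 0.55 of 200 non-fasting patients (0.3%) per day on 12-month accrual, or 3.3 of 200 (1.6%) on the two-month reading. If no unexpected or fatal SAE occurs, nothing changes.
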